1 SYNOPSIS

Title: A Randomized, Double-Blind, Placebo-Controlled Proof-of-Concept Study to Assess the Safety and Efficacy of Elezanumab in Acute Ischemic Stroke	
Background and Rationale:	Elezanumab is an investigational product under development for improvement of neurologic function in patients with acute ischemic stroke. Treatment of acute ischemic stroke patients with elezanumab has the potential to accelerate recovery and/or provide more complete recovery by decreasing neuronal damage and enhancing restoration of neuronal activity.
Objectives and Endpoints:	
The objectives are to assess the efficacy, safety, tolerability, and pharmacokinetics (PK) of elezanumab in subjects with acute ischemic stroke.
 
The primary endpoint is the National Institutes of Health Stroke Scale (NIHSS) total score during the Treatment Period.
 
The secondary endpoint is a favorable outcome based on the modified Rankin Scale (mRS) at Week 52. A favorable outcome is defined as having an mRS score of 0, 1, or 2 at the specified time point.

Investigator(s):	Multicenter
Study Site(s):	Approximately 45 sites in multiple countries.
Study Population and Number of Subjects to be Enrolled:	
Adult male or female, 30 to 90 years of age, inclusive, with a clinical diagnosis of acute ischemic stroke in anterior circulation and able to randomize within 24 hours of "last known normal" (the time before hospital arrival at which time the subject was last known to be without the signs and symptoms of the current stroke or at his or her baseline state of health), supported by acute brain computed tomography (CT) or magnetic resonance imaging (MRI).
 
Approximately 120 subjects will be randomized to receive elezanumab 1800 mg or placebo in a 1:1 ratio.

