- ✓ 7. NIHSS total score of 7 to 21, inclusive. NIHSS eligibility must be confirmed within 1 hour before randomization. For subjects treated with IV tPA \pm EVT, NIHSS must be confirmed \geq 1 hour after completion of all treatments and once any confounding effects of sedation or anesthesia have resolved.
- ✓ 8. No evidence of acute seizure at the onset of index stroke based on assessments conducted per standard of care. Subjects with evidence of seizure at onset of index stroke, but with imaging conclusively demonstrating an acute ischemic stroke are still allowed.
- ✓ 9. No evidence of acute myocardial infarction based on assessments per standard of care (e.g., elevated troponin levels, abnormal ECG).
- ✓ 10. In the judgment of the investigator, symptoms are not considered likely to resolve within the subsequent few hours (e.g., transient ischemic attack [TIA]).

Subject History

- ✓ 11. Subjects or their legally authorized representative confirms that before index stroke, there was no substantial impairment in subject's ability to perform activities of daily living (e.g., dressing, eating, walking, bathing, toileting) without assistance, as defined by a modified Rankin Score (mRS) of 0 to 2 before the index stroke.
- ✓ 12. Subjects with a history of previous stroke more than 3 months before enrollment are allowed if they are no longer experiencing ongoing functional recovery and mRS remains 0 to 2 prior to index stroke.
- ✓ 13. No known history before randomization of clinically significant medical conditions (other than current acute ischemic stroke) or any other reason, including any physical, psychological, or psychiatric condition that in the investigator's opinion would compromise the safety or interfere with the subject's participation in this study, or would make the subject an unsuitable candidate to receive study drug, or would put the subject at risk by participating in the study. Subjects with comorbid conditions that are, in the opinion of the investigator, clinically stable and not expected to meaningfully progress in the following 12 months may be considered eligible.
- ✓ 14. No known medical history of repeated episodes of complex migraine (e.g., weakness, vision, difficulty speaking). Subjects with history of complex migraine, but with imaging conclusively demonstrating an acute ischemic stroke are still allowed.

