7.3 Statistical Analyses for Efficacy

General Considerations

Analysis of the primary, secondary, and all other efficacy endpoints will be conducted on the FAS based on treatment as randomized, unless otherwise specified in the SAP.

The primary and secondary endpoints will be assessed using Bayesian methodology. No formal hypothesis tests will be performed. Additional efficacy endpoints will be summarized using descriptive statistics including the number of observations, mean, standard deviation, minimum, median, and maximum for continuous variables, and number and percent for categorical variables.

For continuous exploratory efficacy endpoints, the between-group treatment summary at each visit will be conducted using a mixed effects model with repeated measures (MMRM) including treatment group, visit, treatment-by-visit interaction, and stratification factors as fixed effects, the baseline values associated with the endpoint as covariates unless otherwise noted in the SAP. Missing data will not be imputed before performing the MMRM.

For binary efficacy endpoints, the frequency and percentage will be provided by treatment group. Missing values will be imputed as non-responders unless otherwise specified in the SAP.

Primary Efficacy Analysis

The primary analysis on NIHSS total score during the Treatment Period will be based on the AUC derived from an MMRM. The monthly-adjusted AUC of NIHSS total score for each treatment group will be obtained using the trapezoidal method and will be adjusted for month by dividing by 12. The MMRM model will include covariates of time since last known normal (≤ 12 hours, > 12 hours based on actual time of study drug initiation), IV tPA use, EVT use, main effects of treatment group and visit, and treatment-by-visit interaction. Each visit by a subject will serve as a repeated measure.

The posterior probability of the treatment group difference (with treatment showing greater improvement than placebo) in monthly-adjusted AUCs being greater than 0.6 using a noninformative prior will be calculated.

Secondary Efficacy Analysis

The secondary efficacy analysis is the proportion of subjects with a favorable outcome based on an mRS at Week 52 of 0, 1, or 2. The posterior probability of the treatment group difference (with treatment showing greater improvement than placebo) in responder rates being greater than 6.25% will be calculated using a non-informative prior.

Additional Efficacy Analyses

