2.3 Treatment Assignment and Blinding

Subjects will be randomized to elezanumab or placebo in a 1:1 ratio. Randomization will be stratified by intravenous (IV) tissue plasminogen activator (tPA) use (yes/no), treatment with endovascular therapy (EVT) (yes/no), and by time since "last known normal" (\leq 11 hours or $>$ 11) at the time of randomization.

The primary analysis of efficacy endpoints will be performed after the last subject completes the Week 52/Premature discontinuation visit. At this time, an interim database lock will occur, the randomization will be loaded into the database and the Data and Statistical Sciences department at AbbVie will perform the statistical analysis. Final safety analyses and post-treatment efficacy analyses will be performed following completion of the post-treatment period and database lock.

Study sites and subjects will remain blinded through the duration of the study.

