3.2 Secondary Endpoint

The secondary endpoint is the proportion of subjects with a favorable outcome based on the modified Rankin Scale (mRS) at Week 52. A favorable outcome is defined as having an mRS score of 0, 1, or 2 at the specified time point.

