8.2 Handling of Missing Data

Missing data will be imputed using the following methods for the efficacy analyses:

- Non-Responder Imputation (NRI): the NRI analysis will categorize any subject who does not have evaluation during a specific visit window as a non-responder for that visit. Unless otherwise noted, this will be the primary approach for accounting for missing data in responder analyses.
- Generalized linear mixed model (GLMM): The model will include a logit link function to compare the probability of having responder between treatment groups of each visit of Day 2-4, Week 4, Week 8, Week 12, Week 24, Week 36, Week 52, and will include baseline NIHSS as a covariate and time from last known normal and initiation of first dose (≤ 12 hours, > 12 hours), tPA use (Y/N), EVT use (Y/N), visit, and treatment group as fixed effects. An unstructured variance covariance matrix will be used. The compound symmetry variance covariance matrix will be used if the model does not converge with unstructured matrix. The GLMM model relies on a missing at random (MAR) assumption.
- As Observed (AO): The AO analysis will not impute values for missing evaluations, and thus a subject who does not have an evaluation on a scheduled visit will be excluded from the AO analysis for that visit. AO will include all values collected in the study.
- MMRM: The repeated measures analysis will be conducted using a mixed model including observed measurements at all visits. The mixed model includes the categorical fixed effects of treatment, visit and treatment-by-visit interaction, main stratification factors at randomization, and the continuous fixed covariates of baseline measurement, unless otherwise noted. An unstructured variance-covariance matrix will be used; if the model does not converge, then a compound symmetry variance-covariance matrix will be used. Denominator degrees of freedom will be computed using the Kenward-Roger method. Parameter estimation is based on the assumption of data being missing at random and using the method of restrictive maximum likelihood. MMRM will be the primary approach in the analysis of continuous

variables unless otherwise noted. The MMRM model relies on a missing at random (MAR) assumption.

For all analyses related to the mRS, if a subject has a value of 6 (dead), this will be carried forward to future visits in the analysis. This will be applied to all mRS analyses, including the responder analysis as observed.

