8.4 Secondary Efficacy Analyses

The point estimate of the responder rate, odds ratio, and corresponding 95% confidence intervals will be derived from a generalized linear mixed model (GLMM) with a logit link function to compare the probability of having responder between treatment groups of each visit of Week 4, Week 8, Week 12, Week 24, Week 36, Week 52. The model will include time from last known normal and initiation of first dose (≤ 12 hours, > 12 hours), tPA use (Y/N), EVT use (Y/N), visit, treatment group as fixed effects, and visit as the random effect by subject. An unstructured variance covariance matrix will be used. The compound symmetry variance covariance matrix will be used if the model does not converge with unstructured matrix.

[figure not shown]

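### Pre-stroke mRS (0, 1 or 2 at entry) is not used or tabulated in any visible mRS analysis, which costs a little precision and hides chance imbalance in a secondary endpoint cut at mRS 0–2

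*Protocol*

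**What the plan says.** **Entry.** Protocol 5.1, criterion 11, requires confirmation of no substantial prior impairment, "as defined by a modified Rankin Score (mRS) of 0 to 2 before the index stroke". Criterion 12 applies the same range to subjects with an earlier stroke, who are allowed "if they are no longer experiencing ongoing functional recovery and mRS remains 0 to 2 prior to index stroke".

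**Endpoint.** SAP 3.2 uses the same scale and cut at Week 52: "A favorable outcome is defined as having an mRS score of 0, 1, or 2 at the specified time point". Protocol 7.3 judges it by the posterior probability of the difference "in responder rates being greater than 6.25% will be calculated using a non-informative prior", and names no covariates.

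**Where the pre-stroke grade could appear but does not:**
- Strata (Protocol 5.8, SAP 2.3): tPA, EVT and time since last known normal only.
- mRS model (SAP 8.4): time to first dose, then "tPA use (Y/N), EVT use (Y/N), visit, treatment group as fixed effects, and visit as the random effect by subject". Baseline NIHSS is also absent.
- General responder GLMM (SAP 8.2): "will include baseline NIHSS as a covariate and time from last known normal and initiation of first dose", plus tPA, EVT, visit and treatment.
- Baseline summaries (SAP 7.1, 7.2, 7.4): demographics, stroke history and MRI, without the grade.
- Subgroups (Protocol 7.3, SAP 8.6): age, sex, NIHSS, time and reperfusion variables.

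**The concern.** Pre-stroke mRS is the pre-event value of the outcome scale itself. With a fixed cut at 2, entry grades 0, 1 and 2 leave room to lose two, one and no grades before the outcome becomes unfavourable. The grade is therefore likely to be prognostic for this endpoint. Baseline NIHSS cannot stand in for it, because it scores the current deficit and not earlier disability. For continuous endpoints the SAP 8.2 MMRM includes the baseline measurement; the binary mRS analysis has no visible counterpart.

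With about 60 subjects per arm, the share entering at grade 2 will differ between arms by chance. In an unadjusted analysis that difference passes into the responder-rate difference in proportion to how prognostic the grade is. If the grade is not tabulated either, a reader of a borderline result cannot check whether the arms started level. Two things are at stake: some precision, and the ability to interpret this one trial.

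**Working it through.** **The plan's own figure.** The sample size ("Approximately 120 subjects will be randomized to receive elezanumab 1800 mg or placebo in a 1:1 ratio") was simulated for the NIHSS AUC. Its inputs are redacted, so it cannot be reproduced, and this point does not dispute it. Only n = 60 per arm is used. The 6.25-point threshold is 0.0625 × 60 = 3.75 responders per arm.

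**Assumptions, none from the documents.** Placebo rate p of mRS 0–2 is 30–50%. Share q in the worse pre-stroke grade is 5–20%, with 40% as an extreme. Loss e in the chance of mRS 0–2 for that grade is 10–40 points.

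**Step 1, standard error of the responder difference.** SE = √(2p(1−p)/60). At p = 40%: √(2 × 0.4 × 0.6/60) = 8.9 points. Over p = 30–50%: 8.4 to 9.1 points.

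**Step 2, chance imbalance.** SD = √(2q(1−q)/60). At q = 5, 8, 12 and 20%: 4.0, 5.0, 5.9 and 7.3 points. The last is 0.073 × 60 = 4.4 subjects.

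**Step 3, shift and precision.** Shift SD = imbalance SD × e. Adjusted SE = √(SE² − shift²), with p = 40%. The last column is the change in the posterior probability, under a flat prior, for a result exactly at the threshold: Φ(shift/SE) − 0.5.

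| q | e | 1-SD shift (points) | SE before → after (points) | SE reduction | Posterior change (points) |
|---|---|---|---|---|---|
| 5% | 10 | 0.4 | 8.94 → 8.94 | 0.1% | 2 |
| 10% | 20 | 1.1 | 8.94 → 8.88 | 0.8% | 5 |
| 20% | 20 | 1.5 | 8.94 → 8.82 | 1.3% | 6 |
| 20% | 30 | 2.2 | 8.94 → 8.67 | 3.0% | 10 |
| 20% | 40 | 2.9 | 8.94 → 8.45 | 5.5% | 13 |
| 40% | 40 | 3.6 | 8.94 → 8.20 | 8.3% | 16 |

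At q = 20% and e = 30, a shift larger than the whole 6.25 points has probability 0.4%. It would need an imbalance of 0.0625/0.30 × 60 = 12.5 subjects.

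**Step 4, bias.** In 200,000 simulated trials (q = 20%, e = 30, p = 40%), the mean estimate equalled the true difference to within 0.01 points. The slope of the estimate on the imbalance was −0.30, which is −e. The imbalance therefore passes into a single trial's estimate but averages to zero.

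**Step 5, realistic models.** Nine simulated scenarios used 60 per arm and these assumptions:
- grade shares 0/1/2 from 80/12/8% to 60/20/20%;
- log-odds lower by 0.3–0.8 at grade 1 and 0.7–2.0 at grade 2;
- treatment odds ratio 1.8;
- NIHSS uniform on 7–21 with slope −0.2.

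Standardised risk differences were compared with and without an ordinal pre-stroke term:
- The ratio of SDs (adjusted to unadjusted) was 0.945 to 1.001, and the gain was about 2.5% or less outside the strongest-effect scenarios. A ratio of 0.947 is worth 120 × (1/0.947² − 1) ≈ 14 subjects; a ratio of 1 is worth none.
- The two estimates within one trial differed with SD 1.1–2.9 points. Leaving NIHSS out of both models, as in the visible SAP 8.4 model, gave 1.1–2.8.
- Adding baseline NIHSS alone cut the SD by about 6–8%, more than pre-stroke mRS did in most scenarios.

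**Step 6, illustration.** With an observed difference of 12 points and SE 9, Φ((12 − 6.25)/9) = 74%. A 2-point shift gives Φ(3.75/9) = 66% or Φ(7.75/9) = 81%. Adjustment moved the estimate by more than 2 points in 7–41% of simulated trials, depending on the scenario.

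**The case against.** The strongest reply is that randomisation already deals with this. The imbalance is zero on average, and the width of the unadjusted posterior includes it. That stands. A reader might infer from the shared cut-point that the comparison is biased; it is not, because unequal chances by entry grade affect both arms alike in expectation.

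A reader might also take the 1.1–2.9 point gap, which is 18–47% of the 6.25-point threshold, as error removed by adjustment. It only measures how far two estimates differ. In the weakest scenario the gap was still 1.1 points while the SD did not improve, and across scenarios the adjusted estimate was closer to the truth in only 52–56% of trials.

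Third, criterion 11 is a range check, and criterion 12 covers only subjects with an earlier stroke. It is tempting to say that every subject's grade must be recorded, but the documents do not say so.

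Fourth, the study is exploratory, with no formal test (Protocol 7.3) and no Type I error control (Protocol 7.6). No decision probability is visible for the 6.25% threshold. This limits the consequence. It also makes the posterior the main summary for this endpoint, so readers should be able to see whether the arms started level.

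Finally, relevant analyses may lie in the redacted text. This stands as a limit on the point.

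**Conclusion.** The point holds as a modest improvement in precision and transparency, not as a threat to validity. No visible part of the plan uses or displays the pre-stroke grade, although the endpoint is cut on the same scale at the top of the entry range. The cost is 0 to about 5% of the SD of the risk difference, usually under 3%. An unseen chance imbalance could move the responder difference by about 1–3 points against an SE of about 9. That is seldom enough to cross 6.25 points by itself, but it can move a borderline posterior by roughly 5–13 percentage points at q = 10–20% and e = 20–40.

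These sizes rest on assumed grade shares, effects and placebo rates, and they would be near zero if few subjects enter above grade 0 or the grade is weakly prognostic. Baseline NIHSS is likely the more valuable covariate, and it is also missing from the visible SAP 8.4 model. The documents do not support saying that the plan never uses the grade: parts of SAP 8.4 and all of 8.5 are redacted, the SAP text for the 6.25% posterior is not visible, and the Operations Manual is not shown.

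**What to change.** 1. **SAP 8.4:** add pre-stroke mRS as one ordinal term (0, 1, 2), together with baseline NIHSS as already used in the SAP 8.2 GLMM, to the fixed effects of the mRS model.
2. **Protocol 7.3 and the matching SAP text:** obtain the 6.25% posterior from the standardised risk difference of a model with the same covariates. Adding a term to the GLMM is not enough, because its visible outputs are responder rates and an odds ratio. Keep the unadjusted posterior as a sensitivity analysis.
3. **SAP 7.2:** tabulate the number and percentage at pre-stroke mRS 0, 1 and 2 by arm. This is worth doing even if the model is left alone.
4. **eCRF:** if only pass or fail is held for criterion 11, add one field for the grade.

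Set this before unblinding. The cost is 1–2 degrees of freedom, a standardisation step to specify and program, one table entry and at most one eCRF field. The conditional odds ratio changes meaning once the covariates enter. No extra visits, procedures or subjects are needed.

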- ✓ 15. No contraindication or inability to tolerate brain MRIs (e.g., a pacemaker or any other implanted device or condition that would preclude proximity to a strong magnetic field).
- ✓ 16. No hypotension requiring the use of IV vasopressor support or systolic blood pressure $<$ 90 mmHg at the time of randomization.
- ✓ 17. No known history within 6 weeks before randomization of active varicella or herpes zoster virus infection or any severe viral infection requiring medical attention.
- ✓ 18. No known currently active drug or alcohol abuse.

- 19. No known receipt of any investigational product within 30 days or 5 half-lives of the drug (whichever is longer) before the first dose of study drug. No current enrollment in another interventional clinical study, including pharmacologic and behavioral interventional studies.
- 20. No known history of prior exposure to elezanumab.
- 21. No known history prior to randomization of an allergic reaction or significant sensitivity to constituents of the study drug and its excipients and/or other products in the same class.

Contraception

- 22. Female who is not pregnant, breastfeeding, or considering becoming pregnant during the study or for within 39 weeks (5 half-lives) after the last dose of study drug.
- 23. For all females of childbearing potential, a negative serum pregnancy test at the Screening Visit and negative serum or urine pregnancy test before all doses of study drug.
- 24. Pregnancy tests are to be performed at home every 4 weeks after the Week 52 visit on women of childbearing potential. A follow-up telephone call to females of childbearing potential will be conducted every 4 weeks to obtain the results of the at-home pregnancy test (not including Weeks 12 or 24) up to 39 weeks (5 half-lives) after the last dose of study drug. Results of pregnancy tests must be documented on the subject's medical record/source.
- 25. Female subjects of childbearing potential must practice at least 1 protocol-specified method of birth control from randomization through 39 weeks (5 half-lives) after the last dose of study drug. Female subjects of non-childbearing potential (see below for definition) do not need to use birth control.

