5.2 Contraception Recommendations

Contraception Requirements for Females

Female subjects must follow the following contraceptive guidelines as specified:

Females, Non-Childbearing Potential

Females do not need to complete serum or urine pregnancy tests, or use birth control during or following study drug treatment if considered of non-childbearing potential due to meeting any of the following criteria:

- Postmenopausal, age > 55 years with no menses for 12 or more months without an alternative medical cause.
- Postmenopausal, age ≤ 55 years with no menses for 12 or more months without an alternative medical cause **and** a follicle-stimulating hormone (FSH) level > 40 IU/L.
- Permanently surgically sterile (bilateral oophorectomy, bilateral salpingectomy, or hysterectomy)

Females of Childbearing Potential

Females of childbearing potential must avoid pregnancy while taking study drug and for at least 39 weeks (5 half-lives) after the last dose of study drug. Females must commit to one of the following methods of birth control:

- Practice true abstinence, defined as: Refraining from heterosexual intercourse when this is in line with the preferred and usual lifestyle of the subject (periodic abstinence [e.g., calendar, ovulation, symptothermal, post-ovulation methods] and withdrawal are not acceptable).
- Combined (estrogen and progestin-containing) hormonal birth control (oral, intravaginal, transdermal, injectable) associated with inhibition of ovulation confirmed to have been initiated at least 1 month before Screening (if already using hormonal birth control).
- Progestin-only hormonal birth control (oral, injectable, implantable) associated with inhibition of ovulation confirmed to have been initiated at least 1 month before Screening (if already using hormonal birth control).
- Bilateral tubal occlusion/ligation, i.e., Essure (can be via hysteroscopy, provided a hysterosalpingogram confirms success of the procedure).
- Intrauterine device (IUD).
- Intrauterine hormone-releasing system (IUS).
- Vasectomized sexual partner (provided the vasectomized partner has received medical confirmation of the surgical success of the vasectomy and is the sole sexual partner of the trial subject).

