5.6 Follow-Up for Subject Withdrawal from Study

Study Drug Discontinuation

For subjects who discontinue the study drug, all efforts should be made to continue conducting all treatment and post-treatment procedures (with the exception of study drug administration) in accordance with the study visit schedule and the subject's continued willingness to participate in order to minimize missing data for efficacy and safety assessments. If a subject discontinued study drug and is unwilling to return to the site, certain assessments may be conducted remotely. At a minimum, subjects should complete the procedures outlined for the Week 52/Premature Discontinuation visit (PD visit), and follow-up visits at 12 and 24 weeks after last dose of study drug. Subjects should be advised on the continued scientific importance of their data even if they discontinue treatment with study drug early.

Withdrawal from the Study

In the event that a subject withdraws or is discontinued from the study, the primary reason for discontinuation and any other reason(s) for discontinuation from the study will be recorded on the appropriate eCRF page. If a subject prematurely discontinues study participation, the procedures outlined for the Week 52/PD visit should be completed as soon as possible, preferably within 2 weeks. In addition, a follow-up phone call 30 days after the last dose of study drug should be attempted to ensure all treatment-emergent AEs/SAEs have been resolved.

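### Criterion 24 starts at-home pregnancy tests at the Week 52 visit but ends them 39 weeks after last dose, so read literally some early stoppers get none (minor, cheap to fix)

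*Protocol*

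**What the plan says.** Four places in the protocol bear on this.

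- **Section 5.1, criterion 24, tests:** "Pregnancy tests are to be performed at home every 4 weeks after the Week 52 visit on women of childbearing potential".
- **Section 5.1, criterion 24, result calls:** telephone calls every 4 weeks cover "the at-home pregnancy test (not including Weeks 12 or 24) up to 39 weeks (5 half-lives) after the last dose of study drug".
- **Section 5.1, criterion 23:** on-treatment testing is tied to dosing, with a "negative serum or urine pregnancy test before all doses of study drug".
- **Section 5.6:** for a subject who stops study drug, "all efforts should be made to continue conducting all treatment and post-treatment procedures (with the exception of study drug administration"). There is also a floor: "At a minimum, subjects should complete the procedures outlined for the Week 52/Premature Discontinuation visit (PD visit), and follow-up visits" 12 and 24 weeks after last dose. Remote contact is possible: "If a subject discontinued study drug and is unwilling to return to the site, certain assessments may be conducted remotely".

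Section 5.2 sets one avoidance period for every woman of childbearing potential, who "must avoid pregnancy while taking study drug and for at least 39 weeks (5 half-lives) after the last dose of study drug". Section 4.1 places the Week 52 visit at study Week 52, and counts the two post-treatment visits and the final 39-week call from the last dose. Section 6.1 likewise collects adverse events until 39 weeks after study drug is discontinued.

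**The concern.** The start and end of the at-home testing period are on different clocks. For a woman who receives all 13 doses they agree: her last dose is at Week 48, the Week 52 visit comes 4 weeks later, and testing fills the rest of her 39 weeks. For a woman who stops early, her 39-week window may close before the Week 52 visit. The rule would then start after it had ended. Criterion 23 does not fill the space, because its tests go with doses and dosing has stopped.

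At stake is how soon a pregnancy would be recognised while drug is still washing out. Section 6.1 requires a pregnancy to be reported within 24 hours of the site becoming aware, so later testing can mean later reporting. No endpoint or statistical analysis is involved.

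**Working it through.** The plan gives no figure to reproduce; the check is calendar arithmetic.

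**Inputs from the protocol.** Doses at Weeks 0, 4, …, 48 and a Week 52 visit at study Week 52 (Section 4.1). At-home tests every 4 weeks after that visit, so at Weeks 56, 60, 64 and so on (criterion 24). Window of 39 weeks after last dose (criterion 24, Section 5.2). Minimum follow-up of the Week 52/PD visit plus visits 12 and 24 weeks after last dose (Section 5.6).

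**Assumptions.** On the minimum path the PD visit is 4 weeks after last dose, and a pregnancy test is done there and at the 12- and 24-week visits. The available text does not confirm either.

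**Formulas.** With last dose at Week s, the window closes at s + 39. At-home tests are those of Weeks 56, 60, … that are no later than s + 39, leaving out s + 12 and s + 24, where a clinic visit falls. The longest untested stretch is the largest interval between neighbours among s, s + 4, s + 12, s + 24, the at-home dates and s + 39.

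| Last dose (week) | Window closes (week) | At-home tests | Longest untested stretch (weeks) |
|---|---|---|---|
| 0, 4, 8, 12 | 39, 43, 47, 51 | 0 | 15 |
| 16 | 55 | 0 | 15 |
| 20 | 59 | 1 | 12 |
| 24 | 63 | 2 | 12 |
| 28 | 67 | 3 | 12 |
| 32 | 71 | 3 | 12 |
| 36 | 75 | 4 | 8 |
| 40 | 79 | 5 | 8 |
| 44 | 83 | 5 | 8 |
| 48 (completer) | 87 | 6 | 4 |

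For a last dose at Week 12 or earlier, the untested stretch runs from Week 24 to Week 39 after last dose: 39 − 24 = 15 weeks, and 15/39 = 38% of the window. The protocol equates 39 weeks with 5 half-lives, so one half-life is 39/5 = 7.8 weeks and the stretch is 15/7.8 = 1.9 half-lives.

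**Sensitivity.**

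- *Visit windows of 7 days.* With a Week 12 dose given at Week 13 and the Week 52 visit held at Week 51, the window closes at Week 52 and the first at-home test is at Week 55: still none. A woman last dosed at Week 16 can gain one test, at Week 55, just as her window closes.
- *PD visit 2 or 6 weeks after last dose.* The 15- and 12-week values do not change.
- *Counting the 12- and 24-week dates as at-home tests.* The exclusion stands only in the sentence on calls. Without it a completer has 8 dates and a woman last dosed at Week 36 has 5. The zeros are unaffected.
- *Reading the start as the Week 52/PD visit, held 4 weeks after last dose.* At-home tests fall 8, 16, 20, 28, 32 and 36 weeks after last dose: 6 tests, longest stretch 4 weeks.
- *On-site tests at every 4-weekly visit.* For a last dose at Week 12 or earlier, the longest stretch is 4 weeks.

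**The case against.** The strongest reply is that the plan, read as a whole, may contain no gap. Section 5.6 and SAP Section 2.3 both name a combined Week 52/premature discontinuation visit, and sites may well read criterion 24 that way. The exclusion of Weeks 12 and 24 points in the same direction: study Weeks 12 and 24 precede Week 52, so it must mean weeks after last dose. Section 5.6 also makes continued visits the default, dropping only the infusion, so pregnancy tests may simply continue. A home test with a telephone call is an obvious candidate for remote assessment. Finally, the Activity Schedule (Appendix D) and Operations Manual (Appendix F) are not in the available text and may settle the matter.

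Most of this stands, and it limits the point. What it does not do is change criterion 24, which names the Week 52 visit alone. Even the combined reading closes the gap only when the PD visit is held early.

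A reader might infer something stronger: that early stoppers go wholly untested for 39 weeks, or that the trial has an established safety gap. The documents do not support either. The zero concerns at-home tests only; the exclusion of Weeks 12 and 24 suggests clinic tests at those visits, and on the stated assumptions these women have 3 tests after last dose. Contraception duties, the 39-week call and adverse event collection also continue.

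**Conclusion.** The point holds as a minor, inexpensive safety improvement. Criterion 24 has mismatched anchors. On its literal wording, a woman of childbearing potential last dosed at Week 12 or earlier who follows only the Section 5.6 minimum has no at-home test in her window. Week 16 is nominally the same but borderline.

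For a last dose at Week 12 or earlier, the longest untested stretch ranges from 4 weeks (no gap) to 15 weeks. The upper end rests on the literal reading, the minimum path, and on-site tests at the PD, 12- and 24-week visits. The lower end applies if sites treat an early PD visit as the starting point or if on-site tests continue every 4 weeks. The missing appendices could also remove the gap.

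The group is probably small: about 120 subjects aged 30 to 90, of whom only women of childbearing potential who stop early and attend only the minimum visits are concerned. Their number is not given and could be zero. Nothing in the efficacy or safety analyses depends on it.

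**What to change.** Reword criterion 24 so that at-home tests and result calls run every 4 weeks after the Week 52/PD visit, begin no later than 8 weeks after the last dose, and continue through 39 weeks after the last dose, with the result obtained on site at the 12- and 24-week post-dose visits. Cross-refer to this in Section 5.6, and check that Appendices D and F agree.

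On the minimum path with a PD visit at 4 weeks, test dates fall at 8, 12, …, 36 weeks after last dose. That is 8 dates, 2 of them on site, leaving 6 at home. With a PD visit at 2 weeks they fall at 6, 10, …, 38 weeks, which is 9 at home. The longest untested stretch drops from 15 weeks to 4, or to at most 8 if the PD visit is late or missed.

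The cost is the wording change plus about 6 to 9 home kits and calls per affected woman. Women still tested at 4-weekly visits would need few or none if those results are accepted in place of home tests. For completers the schedule is essentially the same; the only difference is that the 12- and 24-week results, which current wording leaves open, are assigned to the clinic visit.
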